#### 6.6.1.5. Last Prescribed Dose

For patients on a prophylactic regimen at any time during the study, the last prescribed dose and dosing frequency will be summarized as a cross tabulation of dosing frequency by dose (IU/kg) in which the number and percentage of patients who were last prescribed each combination of dose and dosing frequency (as applicable) will be tabulated. The last prescribed dose will also be summarized for each dosing frequency using descriptive statistics. If no dose (dosing frequency) changes were prescribed, then a patient's starting dose (dosing frequency) will be used. The dose for the twice weekly regimen will be the average of the two doses given. Percentages will be based on the number of patients in each prophylactic regimen (i.e., not on the number of patients in each dosing frequency category). This analysis will not include the ITI period and last prescribed dose for these cases is that before the commencement of ITI.

#### 6.6.2. Compliance

	Statistical Analysis Plan	Final v1.0
---	----------------------------------	-------------------

Dose compliance will be assessed during the efficacy period and will be summarized for the FAS. Except for doses administered in the clinic, study treatment may be administered by a caregiver. Data from the eCRF and EPD will be considered for the analysis of treatment received and patients' compliance with the study protocol.

**6.6.2.1. Compliance in the treatment of bleeding episodes**

Bleeding episodes are defined in Section 5.2.4. All bleeding episodes during the efficacy period for which there is a date and time for both the onset of the bleeding and treatment of the bleeding will be evaluated for compliance. Compliance will first be determined on a per-bleed basis and then on a per-patient basis. That is, compliance for each bleeding episode will be determined and then the overall percentage of bleeding episodes for which treatment was in compliance will be determined for each patient.

The definition of compliance for the treatment of an individual bleeding episode, as specified by the Sponsor, is no more than 8 hours between the onset of the bleed and the initiation of treatment for the bleed. Thus, the compliance rate for the treatment of bleeding episodes will be measured by determining the proportion of injections administered within a maximum of 8 hours of the initial sign of a bleed, as follows:

$$\text{Treatment of bleed compliance rate} = \frac{\text{Number of first injections to treat a bleed taken within 8 hours of the first sign of a bleed}}{\text{Total number of evaluable bleeding episodes}} \times 100$$

The following circumstances result in a bleeding episode being considered not evaluable for the determination of this compliance rate:

- The type of bleed has been classified as Unknown based on the definition of a bleeding episode (>72 hours between consecutive injections) since there is no onset time
- A missing bleed time for a spontaneous or traumatic bleed
- A bleed time that was recorded as being after the time of treatment

Descriptive statistics for compliance to treat a bleeding episode will be presented for the FAS.

**6.6.2.2. Compliance of Prophylactic Injections**

The compliance rate of each patient to the prescribed prophylactic and ITI dosing regimens during the efficacy period will be calculated in 2 ways: As dose compliance and as dosing interval compliance. Compliance will first be determined on a per-injection basis and then on a per-patient basis. That is, compliance for an individual dose or dosing interval will be determined and then the overall percentage of doses and dosing intervals that were in compliance will be determined for each patient.

For the purpose of evaluating compliance, the following will be considered per injection:

- The nominal dose taken compared to the nominal dose prescribed
- The actual day of treatment compared to the prescribed day of treatment

An individual dose will be considered compliant if it is within 80%-125% of the prescribed dose. An individual dosing interval will be considered compliant if the time between two prophylactic doses is within 36 hours of the prescribed dosing interval. Prescribed dose and dosing intervals are according to the Investigator. Instructions provided to the patient by the Investigator regarding dose or dosing interval changes will be used to determine compliance as of the date the information was provided to the patient.

The actual dosing intervals will be calculated as the length of time between consecutive prophylactic doses (date/time of PRx+1 – date/time of PRx), PRx+1 and PRx. The actual time between doses will be determined in minutes and converted to days as the number of minutes divided by 1440. The prescribed dosing interval will be taken from the eCRF as recorded by the Investigator. The absolute value of the difference between the actual and prescribed dosing intervals must be ≤ 1.5 day (+/- 36 hours) in order to be compliant [REDACTED]

All prophylactic injections will be used to determine prophylactic dose compliance; only the prophylactic injections used to determine the average prophylactic dosing interval (i.e., intervals not separated by a bleeding episode or surgical/rehabilitation period), as detailed in Section 5.4, will be used to evaluate prophylactic interval compliance. Dose and dosing interval compliance rates per patient will be determined as follows:

$$\text{Dose compliance rate} = \frac{\text{Number of doses taken within 80\%-125\% of prescribed dose}}{\text{Total number of doses}} \times 100$$

where the percentage of a prescribed dose is calculated as: (nominal dose taken/prescribed dose) ×100 and the “nominal dose taken” will be determined from the nominal potency labeled on the vials used by the patient for each injection of rFIXFc.

$$\text{Dose interval compliance rate} = \frac{\text{Number of doses taken within +/- 36 hours of prescribed day/time}}{\text{Total number of intervals}} \times 100$$

A patient is considered “dose compliant” or “dosing interval compliant” if his respective rate is at least 80%.

Descriptive statistics of the percentage of nominal doses taken per patient within 80%-125% range for dosing compliance as well as frequencies for the dose compliance rate (<80%, ≥80%) will be presented for the FAS. Similarly, descriptive statistics of the percentage of doses taken per patient within ±36 hours [REDACTED] of the prescribed day as well as frequencies of the dosing interval compliance rate (<80%, ≥80%) will be presented for the FAS.

	Statistical Analysis Plan	Final v1.0
---	----------------------------------	-------------------

Based on their per-patient compliance rates for dose and dosing interval (each  $<80\%$ ,  $\geq 80\%$ ), patients will be further classified into the following mutually exclusive categories for overall compliance to their prophylactic treatment as:

- Both dose and interval compliant
- Dose compliant or interval compliant (but not both)
- Neither dose nor interval compliant

#### **6.6.2.3. Compliance of EPD Contemporaneous Data Entry**

Injections must be entered into the EPD within 7 days from the date of the injection. Injections entered outside the 7-day window will be reported as protocol deviations. Descriptive statistics of the percentage of the patients with fewer than 80% of their total individual EPD records entered within this 7-day window and those with  $\geq 80\%$  of records meeting this criteria will be presented for the FAS as well as a summary of % compliance to this criteria by patient.

	Statistical Analysis Plan	Final v1.0
---	----------------------------------	-------------------

## **7. EFFICACY ANALYSIS**

### **7.1. General Efficacy Principles**

Efficacy analyses will be based on the Full Analysis Set and unless otherwise specified, presented by the treatment regimen groups described in Section 5.1.1.

Additionally, the general efficacy and surgical/rehabilitation periods are defined in Section 5.4. Data on bleeding and rFIXFc consumption will be based on the efficacy period; surgical evaluations will be based on the surgical/rehabilitation period.

Analysis of efficacy endpoints that are visit-based will include data from all study visits whether or not in the efficacy period, unless that visit is coincidental with a surgical/rehabilitation period for a major surgery, in which case it would be excluded.

### **7.2. Multiplicity**

Multiplicity is not a concern in this study since no statistical tests are being performed on the efficacy endpoints.

### **7.3. Analysis of Primary Endpoint(s)**

All efficacy endpoints are secondary. Therefore, there will be no analysis of a primary efficacy endpoint.

### **7.4. Analysis of Secondary Endpoints**

#### **7.4.1. Bleeding Episodes**

Bleeding episodes will be recorded in both the EPD and eCRF; this information will be used to derive the secondary efficacy endpoints. During the course of the study the Investigator is given the opportunity to disagree with the type of bleeding (spontaneous, traumatic) as classified by the patient/caregiver, and the patient/caregiver is subsequently given the opportunity to agree or disagree with the reclassification. If the patient/caregiver agrees with the Investigator's assessment, then all analyses subset by type of bleeding will be based on the Investigator's determination of the bleeding type whether or not the change was made to the patient's records.

Standardized definitions of bleeding episodes are provided in 5.2.4.

Bleeding episodes of an unknown type will be included in the determination of the annualized bleeding rate and in summaries based on bleeding episodes but, unless specified otherwise, will not be included in summary tables where endpoints are summarized by type of bleed.

#### **7.4.2. Summary of Bleeding Episodes**

As a description of the raw data collected in this study, the unadjusted number of bleeding episodes per patient will be summarized using descriptive and categorical (e.g. 0, >0-5, >5-10, >10-15, etc.) statistics over all bleeding episodes. Of note, the number of patients with a bleeding

	Statistical Analysis Plan	Final v1.0
---	----------------------------------	-------------------

episode for which the location is unknown will be tabulated in these summaries but no further analysis of unknown bleeding locations is planned.

The total patient years followed during the efficacy period (summed over all patients overall) will be provided in order to put the unadjusted numbers in perspective.

These summaries will be further broken down by bleed type and location. These tables will be presented by treatment regimen as described in Section 5.1.1.

**7.4.3. Annualized Number of Bleeding Episodes per Patient (ABR)**

The per-patient annualized number of bleeding episodes, hereafter referred to as the annualized bleeding rate (ABR), will be calculated for each patient using the following formula:

$$ABR = \frac{\text{Number of bleeding episodes during the efficacy period}}{\text{Total number of days during the efficacy period}} \times 365.25$$

The ABR will be summarized using descriptive and categorical (e.g. 0, >0-5, >5-10, >10-15, etc.) statistics for the FAS. All types of bleeding episodes (spontaneous, traumatic, and type unknown) will be included in determining the annualized number.

These tables will be presented by treatment regimen as described in Section 5.1.1.

This analysis will also be presented by the following subgroups:

- Patients with at least 50 EDs to rFIXFc within a treatment regimen
- Patients with at least 26 weeks of rFIXFc dosing within a treatment regimen
- History of bleeding (estimated frequency of bleeds in prior 3 months: 0, 1-2, 3-5 and >5)
- Patients with no major protocol deviations potentially impacting efficacy (see Section 6.5)

**7.4.4. Annualized Number of Bleeding Episodes per Patient by Type and Location of Bleed**

For completeness, summaries of the ABR will also be provided for the following subsets of bleeds for the FAS:

- Type of bleeding (spontaneous, traumatic, unknown)
- Location of bleeding (joint, muscle, internal, skin/mucosa)
 

For the purpose of analysis bleeding episodes with a location of iliopsoas will be treated as a muscle bleed; however, the location will be displayed as iliopsoas in the listings.
- Location and type of bleeding (joint spontaneous, joint traumatic, muscle spontaneous, muscle traumatic, internal spontaneous, internal traumatic, skin/mucosa spontaneous, skin/mucosa traumatic)

These tables will be presented by treatment regimen as described in Section 5.1.1.

	Statistical Analysis Plan	Final v1.0
---	----------------------------------	-------------------

#### **7.4.5. Assessment of Response to Treatment with rFIXFc for Bleeding Episodes Using the 4-Point Bleeding Response Scale**

Using the EPD, each patient's parent/caregiver rates the treatment response to any bleeding episode using a 4-point scale. Ratings of treatment response are made approximately 8 to 12 hours from the time the injection is given to treat the bleeding episode and prior to any additional doses of rFIXFc given for the same bleeding episode. Response is also assessed by the Investigator and recorded on the eCRF for those patients who are treated in the hospital with rFIXFc for major bleeding episodes.

The 4-point scale is as follows:

- Excellent
- Good
- Moderate
- None

Response categories of excellent and good will be presented combined as well as individually. The number and percentage of injections in each response category will be tabulated based on all injections. Two summaries will be provided. In the first summary percentages will be based on the total number of injections administered for bleeding episodes for which a response was provided. In the second summary percentages will be based on the total number of bleeding episodes whether or not a response was provided.

The assessment of response will also be summarized on a per bleed basis by presenting the number and percentage of first injections to treat a bleeding episode for which the response to the treatment was categorized as excellent, good, moderate, or no response, using both approaches to determine the percentages.

The patient's assessment of response will be summarized for the FAS. In order to evaluate if there is a relationship between compliance to treat a bleed and response to the treatment of the bleed, this endpoint will additionally be summarized by compliance to treat the bleed where compliance will be based on the individual bleeding episodes.

These data will be provided in a listing which will include the total number of bleeding episodes and the number of first injections for which a response assessment was provided.

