10.1.2. Information to be Recorded for Treatment

All rFIXFc injections administered during a study site visit must be recorded in the eCRF. An injection administered during a site visit must not be recorded in the EPD. Injections cannot be logged in both places. All injections performed while the subject is in the hospital at the study site, including doses for surgery, must be recorded in the eCRF.

All rFIXFc injections administered at home by the subject or the parent/caregiver or at locations other than the study site must be entered into the EPD.

CONFIDENTIAL

The information contained herein may not be used, disclosed, or published without the written consent of Bioverativ Therapeutics Inc

The subject or the subject's parent/caregiver must enter dosing information into the EPD *as soon as possible after an injection and within a maximum of 7 days following the injection*, to ensure data integrity, and to facilitate appropriate medical review and dosing guidance. It is recommended that subjects or parents/caregivers enter dosing information immediately after an injection.

The study sites and Clinical Monitors will ensure that there is consistency in dosing information between the subject's medical record, IXRS, source documents, EPD, and eCRFs.

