13.1. Clinical Efficacy Assessments

The following clinical tests/assessments will be performed to assess the efficacy of rFIXFc:

- Recording of bleeding episodes in the eCRF for doses administered at the study site by the Surgeon/Investigator; recording of bleeding episodes in the EPD for doses administered at home by the parents/legal guardians/subjects or at locations other than the study site.
- Assessment of response to bleeding episodes using the 4-point scale by the Investigator for individual bleeding episodes treated at the study site; assessment of all other bleeding episodes in the EPD by the parents/legal guardians/subjects. See [Appendix B](#).
- Physician's global assessment of the subject's response to their treatment regimen using the 4-point scale. See [Appendix C](#).

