16.2.3. Analysis of Efficacy Endpoints

Annualized Bleeding Episodes and Annualized rFIXFc Consumption:

Bleeding episodes during the efficacy period will be annualized on a per-subject basis and summarized by treatment regimen (episodic or prophylaxis regimen) and overall. This ABR will be calculated as the total number of bleeding episodes experienced by a subject divided by the total number of days in their efficacy period for each treatment regimen or overall as appropriate, multiplied by 365.25. The per-subject ABR will also be summarized for type of bleed (spontaneous, traumatic), location of the bleed, and spontaneous joint bleeding episodes, and for other subgroups of interest. The consumption of rFIXFc will be annualized in a similar fashion and summarized overall as well as for subgroups of interest.

Other Efficacy Endpoints:

The number of injections and dose per injection required to resolve bleeding will be summarized on both a per-bleeding-episode and a per-subject basis, where the per-subject basis will be determined as the average over all bleeding episodes for a given subject.

The response to treatment for bleeding will be summarized by the number and percentage of bleeding episodes with each response (excellent, good, moderate, or none).

These data will be summarized overall and for subgroups of interest.

Other Efficacy Assessments:

The total dose administered to resolve a bleeding episode will be calculated and summarized in addition to, and in the same manner as, the specified endpoints of number of injections and dose per injection for resolution of bleeding.

The Investigator's assessment of the subject's overall response to their rFIXFc regimen will be summarized for each study visit and across all visits for the number and percentage of outcomes classified as excellent, effective, partially effective, and ineffective. Summaries will be provided overall.

CONFIDENTIAL

The information contained herein may not be used, disclosed, or published without the written consent of Bioerativ
Therapeutics Inc

Treatment with rFIXFc, bleeding episodes, blood loss, and transfusions administered for major and minor surgeries will be provided in data listings. These assessments will be made during the various components of the surgical/rehabilitation period as appropriate (surgery, postoperative care, and rehabilitation).

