#### **2.2.2. Secondary Endpoints**

The secondary endpoints of the study are as follows:

- The annualized number of bleeding episodes per patient (annualized bleeding rate [ABR]).
- The annualized number of spontaneous joint bleeding episodes per patient.
- Assessments of response to treatment with rFIXFc for bleeding episodes, using the 4-point bleeding response scale (Investigator assessment for bleeding episodes treated in the clinic; parent or caregiver assessment for all other bleeding episodes).
- Total number of EDs per patient per year.
- Total annualized rFIXFc consumption per patient for the prevention and treatment of bleeding episodes.
- The number of injections and dose per injection of rFIXFc required to resolve a bleeding episode.
- rFIXFc incremental recovery (IR).

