Summary of annualized bleeding rate - patients with no major protocol deviations potentially impacting efficacy by treatment regimen
Summary of patient's assessment of response to rFIXFc injections for the treatment of bleeding episodes by treatment regimen
Summary of patient's assessment of response to rFIXFc injections for the treatment of bleeding episodes by compliance to treat the bleed and treatment regimen
Summary of number of injections required for resolution of a bleeding episode by treatment regimen
Summary of dose (IU/kg) of rFIXFc for resolution of bleeds by treatment regimen
Summary of physician's global assessment of the response for episodic and prophylactic regimens
Summary of physician's global assessment of the response for ITI regimens
Summary of health outcomes for episodic and prophylactic regimens
Summary of incremental recovery (IR) (IU/dL per IU/kg) for episodic and prophylactic regimens
ITI
Summary of ITI response
Surgery
Investigators'/surgeons' assessment of patients' hemostatic response to rFIXFc post major surgery
Number of injections and dose required to maintain hemostasis during major surgery
Estimated total blood loss during major surgery
Total rFIXFc consumption (IU/kg) per major surgery
Summary of number of bleeds after surgery per major surgery
Adverse events
Overall summary of rFIXFc treatment-emergent adverse events by treatment regimen
Overall summary of rFIXFc treatment-emergent adverse events by treatment regimen and EPD entry compliance
Summary of rFIXFc treatment-emergent adverse events by treatment regimen
Summary of rFIXFc treatment-emergent adverse events by treatment regimen and EPD entry compliance
Summary of rFIXFc treatment-emergent adverse events by treatment regimen and preferred term in descending order of incidence
Summary of rFIXFc treatment-emergent serious adverse events by treatment regimen
Summary of rFIXFc treatment-emergent adverse events by severity and treatment regimen
Summary of rFIXFc treatment-emergent adverse events by relationship to treatment and treatment regimen
Summary of severe rFIXFc treatment-emergent adverse events by treatment regimen and preferred term in descending order of incidence
Summary of rFIXFc treatment-emergent adverse events leading to treatment discontinuation and/or study withdrawal by treatment regimen
Routine laboratory
Summary of laboratory results and change from baseline for episodic and prophylactic

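### SAP 7.4.5 does not match the two-rater bleed-response endpoint: wherever its analysis text or table titles name a rater, they name only the patient

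*SAP*

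**What the plan says.** **Endpoint.** Protocol 6.2.2 and SAP 2.2.2 define response on the 4-point scale, with the rater set by where the bleed was treated: "Investigator assessment for bleeding episodes treated in the clinic; parent or caregiver assessment for all other bleeding episodes". Protocol 13.1 repeats the split. The rating is made "by the Investigator for individual bleeding episodes treated at the study site", and all other bleeds are rated in the EPD. The Schedule of Events (Protocol 4.2.1) has a separate row for the physician's rating of bleeds treated in clinic.

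**Protocol analysis.** Protocol 16.2.3 sets no limit by rater: "The response to treatment for bleeding will be summarized by the number and percentage of bleeding episodes with each response".

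**SAP analysis.** SAP 7.4.5 first says that the parent or caregiver rates any bleed in the EPD. It then mentions Investigator ratings on the eCRF, but only for patients "treated in the hospital with rFIXFc for major bleeding episodes". The tabulation by injection and the per-bleed summary name no rater. The next paragraph says that the patient's "assessment of response will be summarized for the FAS".

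**Planned tables.** SAP Section 12 has two bleed-response tables. The first is a summary of the patient's "assessment of response to rFIXFc injections for the treatment of bleeding episodes by treatment regimen"; the second has the same subject, split by compliance in treating the bleed.

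**Recording.** Protocol 10.1.2: "An injection administered during a site visit must not be recorded in the EPD".

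**The concern.** Both documents define an endpoint with two raters. Where the SAP's analysis text names a rater, it names one, and where it describes the second rater it narrows that rater's role from clinic-treated bleeds to major bleeds in hospital. A programmer working from SAP 7.4.5 and the table titles could build the tables from diary ratings alone.

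The bleeds affected would not be a random subset, because they are defined by the place of treatment. A response rate without them describes bleeds treated at home or elsewhere off site. That is a different quantity from the secondary endpoint, in a study that plans only about 30 patients.

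**Working it through.** The plan states no figure to reproduce here. The check sets the passages side by side and then works out what the percentages can and cannot show.

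**1. Rater for each kind of bleed**

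| Bleed treated | Rater under the endpoint (Protocol 6.2.2, 13.1; SAP 2.2.2) | Rating described in SAP 7.4.5 |
|---|---|---|
| At home or elsewhere off site | Caregiver | Caregiver, in the EPD |
| At the clinic, major, in hospital | Investigator | Investigator, on the eCRF; use in the tables not stated |
| At the clinic, not major | Investigator | No Investigator rating described; caregiver said to rate any bleed in the EPD |

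Hospital and clinic are not synonyms in these documents. Protocol 7.1 lists administration at the clinic and, separately, in the hospital.

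**2. Could a caregiver rating stand in for the third row?** Protocol 10.1.2 keeps site-visit injections out of the EPD. Protocol 13.1 puts bleeds with doses given at the study site on the eCRF. SAP 7.4.5 ties each rating to an injection, about 8 to 12 hours after it. An EPD rating for a bleed treated only at the clinic may therefore not exist. A bleed treated first at the clinic and then at home could have both ratings.

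**3. Effect on the percentages if Investigator ratings are not used.** Let N be the number of bleeds and f the share treated in the clinic with no caregiver rating.

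- Rated-only summary: the denominator is at most (1 − f)N, all of it caregiver-rated bleeds.
- All-bleeds summary, per-bleed version: each bleed contributes one first injection. The four categories together hold at most (1 − f)N bleeds, so their percentages sum to at most (1 − f)N / N = 1 − f.

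| f (assumed) | Ceiling on the sum of the four categories |
|---|---|
| 5% | 95% |
| 10% | 90% |
| 30% | 70% |

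This ceiling belongs to the per-bleed version. The per-injection version also counts follow-up injections and does not share it.

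**4. Direction of any bias.** Let H be the success rate among caregiver-rated bleeds and C that among clinic-treated bleeds. The endpoint rate is (1 − f)H + fC, and the caregiver-only rate is H. The difference is H − [(1 − f)H + fC] = f(H − C). Its sign depends on whether H exceeds C. The documents give none of f, H and C.

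**5. Declared changes.** SAP Section 10 lists the major departures from the protocol. The rater of bleed response is not among them.

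**The case against.** The strongest reply is that the SAP intends to pool the two sources. SAP 7.4.5 itself acknowledges an eCRF rating ("Response is also assessed by the Investigator and recorded on the eCRF for those patients who are treated in the hospital"). Its main tabulation covers all injections, its per-bleed sentence names no rater, and SAP 7.4.1 says that EPD and eCRF bleeding data both feed the secondary efficacy endpoints. The patient label is also loose: caregivers do the rating in a population of mostly very young children, so the label may say little about whose rating is meant. The sentence on hospital-treated bleeds describes data collection and is not an analysis filter. The table shells, which might settle the matter, are not in the documents.

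This stands to the extent that exclusion of Investigator ratings is inferred. No sentence states it, and a pooled reading is open.

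It does not remove the mismatch. Even on the pooled reading, a non-major bleed treated in the clinic has no clear rating source in SAP 7.4.5: it falls outside the Investigator description there, and its injection may not go into the EPD. Nor does the SAP say how the two sources combine, or which prevails when a bleed has both. The SAP does write such rules elsewhere. SAP 7.4.1 says when the Investigator's classification of bleed type is used, and SAP 7.5.2 and 7.5.3.1 name the Investigator or surgeon for the global and surgical ratings.

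**Conclusion.** SAP 7.4.5 does not match the endpoint it analyses. Its rater-specific wording would not deliver the rating that Protocol 6.2.2 and SAP 2.2.2 define for clinic-treated bleeds. The size depends on f, which the documents do not give. If these bleeds carry no usable rating, the rated-only table describes home-treated bleeds, and the all-bleeds per-bleed percentages are capped at 1 − f.

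A reader might infer three stronger points that the documents do not support:

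- *That the SAP excludes Investigator ratings outright.* It does not say so; see the rater-neutral sentences and SAP 7.4.1.
- *That no listing of these ratings is planned.* SAP 7.4.5 promises a listing, and the listing title in Section 12 names no rater. Only the two tables are labelled as the patient's.
- *That the tables would overstate response.* If H = 90% and C = 75% are assumed, f(H − C) is 0.10 × 15 = 1.5 points to 0.40 × 15 = 6 points too high for f of 10% to 40%. If C = 95% is assumed instead, it is 0.10 × (−5) = −0.5 to 0.40 × (−5) = −2 points, an understatement. All these inputs are invented, so no direction can be claimed.

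The stakes are bounded. This is a descriptive secondary endpoint with no hypothesis test, and the primary endpoint, inhibitor development, is untouched. The correction is still worth making, because it is specific and needs no new data.

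**What to change.** Amend SAP 7.4.5 before database lock as follows:

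1. State that each bleed uses its endpoint-defined rater: the Investigator's eCRF rating if treated at the study site, the caregiver's EPD rating otherwise.
2. Add a rule for bleeds that have both ratings, such as those treated first at the clinic and then at home.
3. Present the response tables pooled and by rater, so that the clinic-treated share is visible.
4. Reconcile the wording on major bleeds in hospital with Protocol 6.2.2, Protocol 13.1 and SAP 2.2.2.
5. Retitle the two tables in SAP Section 12 so that they no longer name only the patient.

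The cost is SAP wording and a merge of the eCRF rating with the EPD rating. The protocol already schedules collection of both.
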